#### 9. STUDY PROCEDURES

Table 1 outlines the timing of procedures and assessments to be performed throughout Part A of the study, once written informed consent has been obtained from the subject. Section 10.13 specifies laboratory assessment samples to be obtained. The schedule of visit dates should be established, either prior to or at the time of screening to allow subjects an opportunity to assess whether there are likely to be significant conflicts with other activities or planned absences. To the extent possible, subjects will be expected to adhere to the visit schedule, and any rescheduling of visits must be agreed, in advance, with the investigator and sponsor.

The investigator may, at his/her discretion, arrange for a subject to have an unscheduled assessment, especially in the case of AEs that require follow-up or are considered by the investigator to be possibly related to the use of study drug. The unscheduled visit page in the eCRF must be completed.

Study discontinuation procedures are described in Section 7.2.1.

Details regarding participation in Part B, the long-term extension, are provided in the appendices (Section 15).

Table 1: Schedule of Activities for Part A

Study Period	per	ening iod						Main period  Noncontrolled portion									Follow-up perio		s)
	8 we	eks) bjects A		Contr	olled p	ortion											All subjects not entering Part B		
Study Week	−8 to −4	-2	1	2	4	8	12	14 B	16	20	24	30	36	42	48	52	54	56	60 Exit
Study Day	–56 to –28	-14	1	14	28	56	84	98	112	140	168	210	252	294	336	364	378	392	420
Study Visit	1	2	3	4	5	6	7	8	9	10	11	12	13	14	15	16	17	18	19
Visit window (± days)	N/.	A C	0	3	3	7	7	7	7	7	7	7	7	7	7	7	3	3	7
Informed consent	X																		
Demographics	X																		
Medical history	X																		
Inclusion/exclusion D	X	X	X																
Vaccination E		X				X													
Concomitant medications	х	X	X	X	X	X	X	X	x	Х	Х	X	X	X	X	X	X	X	X
Physical examination F	X	X	X	X	X	X	X	X	X	X	X	X	X	X	X	X	X	X	X
12-lead ECG	X		X	X	X	x	x	X	X	x	x	X	X	X	X	x	X	X	X
Renal biopsy G	2	ζ.		X X															
Randomization			X																
Pegcetacoplan administration B				Group 1 only				All subjects											
Infusion site/pump safety assessment H				Group 1 only				All subjects											

Table 1: Schedule of Activities for Part A

Study Period	per (up	o to		Main period									(8	Follow-up period (8 weeks)					

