# 9.2.1.2. Group 1 Subjects Only

- PK collection: collect after blood sample draws and before dosing
- · Dispense investigational product and infusion materials
- Train subject to perform home infusion

- Administer pegcetacoplan to subjects
- Infusion site/pump safety assessment
- Additional vital sign measurement at 30 minutes (±5 minutes) after dosing

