# 9.2.3. Visit 7 or 8 (Week 12 or 14)

Depending on when the Group 2 subjects receive their Week 12 renal biopsies (see Section 9.2.2), the following will occur at either Visit 7 or 8 (Week 12 or 14). The following assessments will be performed and information collected as noted above, as outlined in the Schedule of Activities (Table 1). Please note the few items that are specific to treatment group; Group 1 will not have to do all the same assessments as Group 2.

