# 10.3. Vital Signs

Vital signs (body temperature, respiration rate, heart rate, and systolic and diastolic blood pressure measurements) will be evaluated at the visits indicated in the Schedule of Activities (Table 1). All vital signs will be measured after the subject has been resting in a sitting position for at least 5 minutes, except when they are supine or semireclined because of study procedures and/or AEs, or if deemed necessary by the investigator. Blood pressure measurements are to be taken in the same arm for the duration of the study. Body weight (without shoes) will be recorded whenever vital signs are recorded; height (without shoes) will be recorded at screening only.

Vital signs measurements will be repeated if clinically significant or if machine/equipment errors occur. Out-of-range blood pressure, respiratory rate, or heart rate measurements will be repeated, at the investigator's discretion. Any confirmed, clinically significant vital signs measurements must be recorded as AEs

When pegcetacoplan is administered at the study site, vital signs will be measured within 2 hours prior to infusion, before venipuncture and ECG. Following the first infusion, vital signs will be measured again at 30 minutes (±5 minutes) after dosing. For subjects in Group 2, vital signs will be measured once at each visit during the controlled period.

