3.5. Analysis Timing

The analysis of data from the Part A Controlled Portion of the study will be performed when all subjects have completed the Part A Controlled Portion or discontinued early and all corresponding data have been entered into the database, reviewed, cleaned, and finalized, and the Week 12 Analysis database locked. At that time, the primary analysis will be performed, which will include all efficacy and safety analyses for the Part A Controlled Portion. For Week 12 Analysis, all summary tables will be presented by randomized group.

The analysis of data from the Part A Non-Controlled Portion will be performed once all subjects have completed the Part A Non-Controlled Portion or discontinued early and all corresponding data have been entered into the database, reviewed, cleaned, and finalized, and the Week 52 Analysis database locked. For disposition, baseline summary, and efficacy analysis, tables will be presented similarly as Week 12 Analysis.

The table summaries for protocol deviations, concomitant medications, study drug exposure and compliance, as well as all AE summaries will be presented in 5 columns: (1) Group 1's Part A Controlled Portion results; (2) Group 1's Part A Non-Controlled Portion results; (3) Group 2's Part A Non-Controlled Portion results; (4) Part A Non-Controlled Portion results combined (in other words, combining columns 2 and 3); (5) for all results since Pegcetacoplan injection (in other words, combining columns 1 and 4). More details on the summary layout are provided in the separate table shell document.

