7.3. Vital Signs

Observed and change from baseline in vital signs (pulse rate, respiratory rate, systolic and diastolic blood pressure, temperature, and weight) will be summarized by treatment group and overall at each analysis visit.

Additionally, the number and percentage of subjects with post-baseline potentially clinically significant (PCS) vital sign values will be tabulated. Vital signs are potentially clinically significant (PCS) if they meet the PCS criteria listed in the table below:

Table 2: Criteria for Potentially Clinically Significant Vital Signs

VS parameter	Criteria
HR	≥100 BPM <40 BPM
SBP	≥130 mm Hg ≥160 mm Hg ≥ 180 mm Hg ≥20 mm Hg increase from baseline <90 mm Hg ≥20 mm Hg decrease from baseline
DBP	≥90 mm Hg ≥15 mm Hg increase from baseline <40 mm Hg post-baseline ≥15 mm Hg decrease from baseline
Temp	≥ 38°C

All vital sign values and change from baseline values will be listed. In the listing, potentially clinically significant vital sign values will be flagged.

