13.5. Repeated or Unscheduled Assessments of Safety Parameters

For safety parameters, if a subject has repeated assessments before the start of investigational product, then the results from the final assessment made prior to the start of investigational product will be used as baseline. If end of study assessments are repeated or unscheduled, the last post-baseline assessment will be used as the end of study assessment for generating descriptive statistics. However, all post-baseline assessments will be used for Potentially Clinically Significant (PCS) value determination and all assessments will be presented in the data listings.

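### The Week 12 vital-sign PCS table counts every post-baseline reading, and Group 1 has one more scheduled set than Group 2 (5 vs 4), which slightly inflates its flagged percentage

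*SAP*

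**What the plan says.** **What is counted.** SAP Section 7.3 says that "the number and percentage of subjects with post-baseline potentially clinically significant (PCS) vital sign values will be tabulated". SAP Section 13.5 adds that "all post-baseline assessments will be used for Potentially Clinically Significant (PCS) value determination". The rule in SAP Section 13.4 that picks one value per visit window therefore governs the by-visit summaries but does not limit the PCS count.

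**How it is shown.** SAP Section 3.5 says: "For Week 12 Analysis, all summary tables will be presented by randomized group".

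**What is measured.** Protocol Section 10.3, repeated in Table 1 footnote I, says: "Following the first infusion, vital signs will be measured again at 30 minutes (±5 minutes) after dosing". It continues: "For subjects in Group 2, vital signs will be measured once at each visit during the controlled period". Protocol Section 9.2.1.2, which covers Group 1 only, lists for the randomization visit "Additional vital sign measurement at 30 minutes (±5 minutes) after dosing". Group 2 has its own 30-minute set at its first dose, which Protocol Section 9.2.3 places at Visit 7 or Visit 8, depending on when the Week 12 biopsy is done.

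**What is baseline.** Under SAP Section 13.3, baseline in Group 1 is the last value before the first dose. In Group 2 it is the last value up to and including the day of randomization.

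Neither document excludes the 30-minute set from the PCS table or shows it separately.

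**The concern.** The percentage of subjects ever flagged rises with the number of readings. If one arm is read more often, its percentage is higher even when every reading carries the same risk in both arms. Weeks 1 to 12 are the only period in which randomized treated and untreated subjects can be compared on safety, and the Week 12 table puts the two percentages side by side. Several vital-sign thresholds in SAP Table 2 are not extreme (systolic pressure of at least 130 mm Hg, heart rate of at least 100, a rise or fall of 15 to 20 mm Hg), so flags need not be rare. The extra reading is also taken shortly after an infusion, so it differs in kind from a visit value taken before dosing. At stake is how a descriptive safety table is read. No error rate or formal conclusion is involved.

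**Working it through.** **Step 1. Count the scheduled post-baseline sets in the controlled portion** (Protocol Table 1, Sections 9.2.1.2 and 10.3; baseline from SAP Section 13.3).

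| Time | Group 1 | Group 2 |
|---|---|---|
| Day 1, before dose / single set | baseline | baseline |
| Day 1, 30 min after infusion | 1 | none |
| Weeks 2, 4, 8, 12 | 4 | 4 |
| Post-baseline total | 5 | 4 |

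The imbalance is one set in total, not one per visit. The count uses the Section 13.3 baseline. For repeated safety assessments, SAP Section 13.5 instead takes the last value before the start of investigational product. Read literally, that would move Group 2's baseline to its first dose and leave it almost no post-baseline readings in this portion, so the two sections should be aligned.

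**Step 2. Effect on the percentage ever flagged, with no drug effect.** The plan states no PCS rate, so there is no figure of its own to reproduce. Let p be the assumed chance that one reading is flagged, equal in both groups and at every time point. With independent readings:

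- P(at least one flag) = 1 - (1-p)^k, with k = 5 in Group 1 and k = 4 in Group 2
- Excess = (1-p)^4 - (1-p)^5 = p(1-p)^4

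| p (assumed) | Group 1 | Group 2 | Excess (points) |
|---|---|---|---|
| 0.01 | 4.9% | 3.9% | 1.0 |
| 0.05 | 22.6% | 18.5% | 4.1 |
| 0.10 | 41.0% | 34.4% | 6.6 |
| 0.20 | 67.2% | 59.0% | 8.2 |
| 0.30 | 83.2% | 76.0% | 7.2 |
| 0.50 | 96.9% | 93.8% | 3.1 |

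At p = 0.10, for example, 0.10 × 0.90^4 = 0.0656. The maximum is at p = 0.20, where 0.20 × 0.80^4 = 0.0819.

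**Step 3. Allow for correlation within a subject.** Independence is the least plausible case for repeated blood pressures in one person. A beta-binomial model with mean p and within-subject correlation r gives:

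| p (assumed) | r = 0.3 | r = 0.5 |
|---|---|---|
| 0.05 | 1.6 points | 0.9 points |
| 0.10 | 2.8 points | 1.6 points |
| 0.20 | 4.1 points | 2.6 points |

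**Step 4. Put this beside the sample size.** With at most 9 and 3 subjects, one Group 2 subject is 1/3 = 33 points and one Group 1 subject is 1/9 = 11 points. The largest excess is 0.0819 × 9 = 0.74 of a Group 1 subject. At p = 0.10 with independent readings, the standard error of the difference is √(0.41 × 0.59/9 + 0.344 × 0.656/3), about 32 points.

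**Step 5. Group 2 at Visit 7.** Visit 7 is Day 84 ± 7, that is Days 77 to 91. SAP Section 13.4 assigns Day 70 to before Day 91 to Week 12 and labels it controlled portion. A Group 2 subject first dosed at Visit 7 on Days 77 to 90 would have a 30-minute set inside that window, giving five sets, one of them on treatment in the column meant to be untreated. Protocol Section 8.2 says Group 2 dosing does not begin until Week 13. The SAP does not say whether the window or the first dose ends the portion. These passages need to be reconciled.

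**The case against.** The strongest reply is that the effect is too small to matter. The study is descriptive, with no hypothesis test. A bias of a few points cannot be seen against a standard error of about 32 points. SAP Section 7.3 lists every value and flags the PCS ones, so with at most 12 subjects a reader can trace any flag to the Day 1 post-infusion reading. Counting all readings is a deliberate, sensitivity-first safety choice, and the post-infusion set is genuine on-treatment data. The table layouts are in a separate document not available here and may already separate time points. All of this stands. It limits the priority of the point but does not remove the 5 vs 4 imbalance, which runs in a known direction and which neither document addresses.

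A reader might infer three stronger things that the documents do not support.

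- **That Group 2 can never have a post-infusion set in the controlled-portion table.** Step 5 shows that it can if first dosed at Visit 7.
- **That unscheduled readings push flags toward Group 1.** Protocol Section 9 leaves these to the investigator's discretion, especially for "AEs that require follow-up or are considered by the investigator to be possibly related to the use of study drug". Need for follow-up applies to untreated subjects too, and the repeats of abnormal vital signs in Protocol Section 10.3 apply to both groups. No direction can be shown.
- **That the laboratory and ECG PCS tables share the problem.** The visit schedule is the same in both groups, and Protocol Section 10.5 takes ECGs once, before dosing. No scheduled imbalance has been shown there.

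**Conclusion.** The point holds in a narrow form and is of low priority. In the Week 12 by-group vital-sign PCS table, Group 1 has five scheduled post-baseline sets and Group 2 has four, so Group 1's ever-flagged percentage is slightly too high for a like-for-like comparison. With no drug effect the excess is 6.6 points at an assumed p of 0.10 and at most 8.2 points at 0.20 if readings are independent. It is about 1 to 4 points with correlation of 0.3 to 0.5 and p between 0.05 and 0.20. This rests on the SAP Section 13.3 baseline, on an equal flag probability at every reading including the one after infusion, and on no Group 2 first dose inside the Week 12 window. If such a dose occurs, that subject's count is also five and the Group 2 column is no longer purely untreated. It would go too far to conclude that the table misleads materially: the artefact is worth less than one Group 1 subject, and no inference depends on it.

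**What to change.** In SAP Sections 7.3 and 13.5:

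- Base the Week 12 between-group vital-sign PCS table on the scheduled visits common to both groups (Weeks 2, 4, 8 and 12), using pre-dose values and, for Group 2, only values before its first dose.
- Show PCS values from the 30-minute post-infusion set on a separate row, taken at each group's own first infusion.
- Keep the all-assessment PCS count, including unscheduled values, as a supplementary table and in the listings.

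Both groups then have four scheduled sets and the same expected percentage under no drug effect (34.4% in each at p = 0.10 with independent readings). The rule also keeps a Visit 7 post-infusion reading out of the untreated column. The laboratory and ECG PCS tables need no change on this ground.

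The cost is SAP wording and one table layout, with no new data. The downside is that the comparison table leaves out a few readings, all of which remain visible elsewhere.

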13.6. Handling of Missing, Unused, and Spurious Data

13.6.1. Missing Date of Investigational Product

When the date of the last dose of investigational product is missing for a subject in the Safety Set, all efforts should be made to obtain the date from the investigator. If it is still missing after all efforts, then the last visit date will be used in the calculation of treatment duration.

13.6.2. Missing Date Information for Prior or Concomitant Medications

When the start date and the stop date are both incomplete for a subject, impute the start date first.

13.6.2.1. Incomplete Start Date

The following rules will be applied to impute the missing numerical fields. If the stop date is complete and the imputed start date is after the stop date, then the start date will be imputed using the stop date.

- Missing Day and Month
 - If the year of the incomplete start date is the same as the year of the date of Study Day 1, then the day and month of the date of Study Day 1 will be assigned to the missing fields
 - If the year of the incomplete start date is before the year of the date of Study Day 1, then December 31 will be assigned to the missing fields
 - If the year of the incomplete start date is after the year of the date of Study Day 1, then 01 January will be assigned to the missing fields.
- Missing Month Only
 - The day will be treated as missing and both month and day will be replaced according to the above procedure.
- Missing Day Only
 - If the month and year of the incomplete start date are the same as the month and year of the date of Study Day 1, then the day of the date of Study Day 1 will be assigned to the missing day
 - If either the year is before the year of the date of Study Day 1 or if both years are the same but the month is before the month of the date of Study Day 1, then the last day of the month will be assigned to the missing day
 - If either the year is after the year of the date of Study Day 1 or if both years are the same but the month is after the month of the date of Study Day 1, then the first day of the month will be assigned to the missing day

13.6.2.2. Incomplete Stop Date

The following rules will be applied to impute the missing numerical fields. If the date of the last dose of investigational product is missing, then replace it with the last visit date. If the imputed stop date is before the start date (imputed or non-imputed start date), then the imputed stop date will be equal to the start date.

- Missing Day and Month
 - If the year of the incomplete stop date is the same as the year as of the date of the last dose of investigational product, then the day and month of the date of the last dose of investigational product will be assigned to the missing fields
 - If the year of the incomplete stop date is before the year of the date of the last dose of investigational product, then 31 December will be assigned to the missing fields
 - If the year of the incomplete stop date is after the year of the date of the last dose of investigational product, then 01 January will be assigned to the missing fields.
- Missing Month Only
 - The day will be treated as missing and both month and day will be replaced according to the above procedure.
- Missing Day Only
 - If the month and year of the incomplete stop date are the same as the month and year of the date of the last dose of investigational product, then the day of the date of the last dose of investigational product will be assigned to the missing day
 - If either the year is before the year of the date of the last dose of investigational product or if both years are the same but the month is before the month of the date of the last dose of investigational product, then the last day of the month will be assigned to the missing day
 - If either the year is after the year of the last dose of investigational product or if both years are the same but the month is after the month of the date of the last dose of investigational product, then the first day of the month will be assigned to the missing day.

13.6.3. Missing Date Information for Adverse Events

For AEs with partial start dates, non-missing date parts will be used to determine if the AE is treatment-emergent or not. If a determination cannot be made using the non-missing date parts as to when the AE occurred relative to study drug administration, e.g. AE start year and month are the same as the year and month of the first dose of investigational product, then the AE will be classified as treatment-emergent.

To facilitate categorization of AEs as treatment emergent, imputation of dates can be used. For AEs, the default is to only impute incomplete (i.e., partially missing) start dates. Incomplete stop dates may also be imputed when calculation of the duration of an AE is required per the protocol. If imputation of an incomplete stop date is required, and both the start date and the stop date are incomplete for a subject, impute the start date first.

- Rules to impute incomplete start date are the same as stated in Section 13.6.2.1.
- Rules to impute incomplete stop date are the same as stated in Section 13.6.2.2.

13.6.4. Missing Severity Assessment for Adverse Events

- If severity is missing for an AE starting prior to the date of Study Day 1, then a severity of “Mild” will be assigned.
- If the severity is missing for an AE starting on or after the date of Study Day 1, then a severity of “Severe” will be assigned.

The imputed values for severity assessment will be used for incidence summaries, while the actual values will be used in data listings.

13.6.5. Missing Relationship to Investigational Product for Adverse Events

If the relationship to investigational product is missing for an AE starting on or after the date of Study Day 1, a causality of “Related” will be assigned.

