#### 8.2. Dosage Selection

The dose of pegcetacoplan is 1080 mg twice per week via SC infusion (20 mL) during the main period of Part A (with dosing not beginning for Group 2 until Week 13) and during Part B. As noted in Section 4.2.1, this study uses the same 1080 mg twice weekly dosing schedule currently used in the Phase 3 studies in patients with PNH. This dose was also evaluated in Study APL2-201, a Phase 2 study that enrolled patients with C3G.

Group 1 subjects will receive their initial doses of pegcetacoplan at the scheduled clinic visit on Day 1 and will continue to receive their pegcetacoplan (1080 mg/20 mL twice a week) on Day 1 and Day 4 of each treatment week until Week 52 if they do not enter Part B; however, if they do enter Part B, the treatment schedule will continue as during Part A.

Group 2 subjects will receive their initial doses of pegcetacoplan after the Week 12 renal biopsy (see Schedule of Activities [Table 1]) and will continue to receive pegcetacoplan (1080 mg/20 mL twice a week) on Day 1 and Day 4 of each treatment week until Week 52 if they do not enter Part B; however, if they do enter Part B, the treatment schedule will continue as during Part A.

Dosing diaries will be utilized for pegcetacoplan and are to be completed for each dose administered at the clinic or outside regular clinic visits. Subjects should ideally maintain a consistent dosing schedule and should not delay or defer dosing. Missed doses will be handled on a case-by-case basis between the investigator and medical monitor, with the general approach being to administer a missed dose as soon as noticed, unless the next dose has already been administered.

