Urine pregnancy test		X	X	X	X	X	X	X	X	X	X	X	X	X	X	X	X	X	X
FSH, HIV, HCV, HBsAg, HBcAb R	х																		
AEs	Х	X	х	Х	Х	Х	X	X	Х	Х	Х	X	Х	X	X	X	X	X	X
Post-transplant immunosuppression plan documentation		x																	
Ophthalmologic evaluation (optional) S		XS													XS				

Abbreviations: ADA = antidrug antibodies; AE = adverse events;  $\beta$ -HCG =  $\beta$ -human chorionic gonadotropin; CDC = Centers for Disease Control and Prevention;

NOTE: When multiple assessments/procedures occur at the same time, order should be: vital signs, ECGs, blood collection/sampling, pegcetacoplan dosing.

CKD-EPI = Chronic Kidney Disease-Epidemiology Collaboration; ECG = electrocardiogram; eGFR = estimated glomerular filtration rate;

FSH = follicle-stimulating hormone; GFR = glomerular filtration rate; HBcAb = hepatitis B core antibody; HBsAg = hepatitis B surface antigen;

HCV = hepatitis C; N/A = not applicable; PK = pharmacokinetic(s); RBC = red blood cell; SC = subcutaneous;

SD-OCT = spectral domain optical coherence tomography.

A. Subjects who meet the medical history requirements will enter the screening period at Visit 1 and return for Visit 2, but all Visit 2 assessments need not occur in a single visit and Visit 2 can be split into multiple visits (eg, 2a, 2b).

- B. Subjects will self-administer SC pegcetacoplan after receiving appropriate training and sign-off by a research nurse or other personnel in their first treatment week. During site visits subjects will self-administer pegcetacoplan at the site, with the exception of the very first dose. Group 2 subjects will be trained on self-administration of pegcetacoplan and receive their supply of pegcetacoplan at the next scheduled clinic visit (Visit 7 or 8) following their biopsies.
- C. Visit 2 must occur at least 7 days after Visit 1 and at least 14 days prior to the Day 1 dosing date; the vaccinations and biopsy can occur any time after confirmation of eligibility based on Visit 1 data.
- D. Specific inclusion/exclusion criteria will be measured during screening, and some of them require confirmation prior to any activities of Day 1. See the inclusion/exclusion criteria in Section 7 for further detail.

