4.3. Safety Set

The safety set includes all subjects who receive at least 1 dose of pegcetacoplan, and subjects who are randomized into Group 2.

All safety analyses will be conducted using the safety set.

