7. SAFETY ANALYSIS

7.1. Adverse Events

Treatment-emergent adverse events (TEAEs) are defined as those AEs that develop or worsen after the first dose of study medication (or after randomization in Group 2) and up to 56 days beyond the last dose of study medication. Analysis of AEs (as discussed below) will be limited to TEAEs, but data listings will include all AEs regardless of their timing.

All reported AEs will be coded using the current version of MedDRA and summarized by System Organ Class (SOC) and Preferred Term (PT). All summaries by SOC and PT will be ordered by decreasing frequency of subjects within each SOC and then similarly by decreasing frequency of subjects within each PT. In the case of equal frequency of number of subjects in SOC or PTs, summaries of TEAEs will be sorted alphabetically. Rules for handling missing severity, relationship to study drug, relationship to infusion procedure, outcome, and missing dates of AEs are described in Section 13.

If a PT was reported more than once for the same subject, that subject would only be counted once in the incidence for that PT. For subjects experiencing the same PT at multiple severities, the occurrence of the AEs with the greatest severity will be used in the analysis of incidence by severity. For subjects experiencing the same PT at multiple relationship levels, the occurrence of the AEs with the strongest relationship to study drug will be used in the analysis of incidence by relationship to study drug.

The AE summaries will be presented by treatment group and overall. The number and incidence of rejection episodes and graft loss will also be summarized.

An overall summary for TEAEs including number of subjects who experience a TEAE, number of total TEAEs and number of unique TEAEs will be provided:

- TEAE
- Treatment-related TEAE
 - Related
 - Not related
- Infusion-related TEAEs
 - Related
 - Not related
- Serious TEAE
- Maximum severity of TEAEs
- Infusion site reaction (yes/no)
- TEAE leading to treatment discontinuation
- TEAE leading to dose interruption
- TEAE leading to study discontinuation
- TEAE leading to death

The following summaries will be provided:

- TEAEs by SOC and PT
- TEAEs by PT in decreasing order of frequency
- Treatment-related TEAEs by SOC and PT
- Infusion-related TEAEs by SOC and PT
- Serious TEAEs by SOC and PT
- TEAE by SOC, PT and maximum severity
- TEAE leading to treatment discontinuation by SOC and PT

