- TEAE leading to dose interruption by SOC and PT
- TEAE leading to study discontinuation by SOC and PT
- TEAE leading to death by SOC and PT

The following listings will be provided:

- All AEs
- Serious Adverse Events (SAEs)
- AEs leading to study drug discontinuation
- Death
- Treatment-related Adverse Events
- Infusion-related Adverse Events

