13.3. Definition of Baseline

For all evaluations unless otherwise noted, baseline is defined as the most recent non- missing measurement prior to the first administration of study drug (Study Day 1 for treatment group 1), or prior to/on the randomization date (Study Day 1 for treatment group 2). Baseline can be the same date as first dose, given the measurement is expected prior to first dose when only date information is available.

In by-visit summary tables, the baseline will be summarized using all available data, but also for each visit using only the baseline data from subjects with available data at the visit; hence the mean change from baseline will equal the mean visit value – mean baseline value.

Throughout this document ‘change from baseline’ refers to the actual change from baseline (i.e. visit value – baseline value).

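### SAP 13.6.5 would tabulate an adverse event with missing causality as treatment-related in a Group 2 subject who has not yet received pegcetacoplan

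*SAP*

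**What the plan says.** SAP 13.6.5 has a single rule. Where the relationship to investigational product "is missing for an AE starting on or after the date of Study Day 1, a causality of" *Related* is assigned. It does not mention treatment group or whether the subject has been dosed.

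Four other provisions determine how that rule works for Group 2:

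- SAP 13.3 places the Group 2 baseline "prior to/on the randomization date (Study Day 1 for treatment group 2", which ties Study Day 1 to randomization and not to first dose.
- Protocol 8.2 describes the main-period regimen "with dosing not beginning for Group 2 until Week 13". Footnote B of Protocol Table 1 says Group 2 subjects "receive their supply of pegcetacoplan at the next scheduled clinic visit (Visit 7 or 8) following their biopsies".
- SAP 4.3 defines the Safety Set as "subjects who receive at least 1 dose of pegcetacoplan, and subjects who are randomized into Group 2". SAP 7.1 and Protocol 12.4 both count Group 2 treatment-emergent events from randomization.
- SAP 7.1 plans a table of "Treatment-related TEAEs by SOC and PT" and a separate listing of "Treatment-related Adverse Events". SAP 3.5 presents the Week 12 tables by randomized group.

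For severity, the neighbouring SAP 13.6.4 adds: "The imputed values for severity assessment will be used for incidence summaries, while the actual values will be used in data listings". SAP 13.6.5 has no matching sentence.

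**The concern.** Assigning *Related* to a missing causality is a sensible worst-case convention once a subject has received drug. Before the first dose it cannot be correct, because an event cannot be caused by a drug the subject has not had. SAP 13.6.5 makes no distinction, since its trigger is Study Day 1, which in Group 2 precedes exposure by about three months.

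The result would appear in the control column of the trial's only randomized comparison. There the convention is not conservative: a false entry raises the control rate and narrows any excess seen in Group 1. With at most three controls, one entry would be conspicuous and would need explaining in the study report.

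The text also leaves open whether an imputed *Related* would put the subject in the separate listing of treatment-related events.

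**Working it through.** The plan gives no figure to reproduce. The check follows the rule through the documents and then sizes one occurrence.

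**Trace for a Group 2 event with missing causality that starts after Day 1 and before first dose**

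1. Is it treatment-emergent? Yes. The Group 2 window opens at randomization (SAP 7.1, Protocol 12.4).
2. Is the subject in the Safety Set? Yes, by randomization alone (SAP 4.3).
3. Does the imputation apply? Yes. The event starts after Study Day 1, which is randomization (SAP 13.3, 13.6.5).
4. Has the subject been exposed? No. Group 2 cannot start pegcetacoplan until the Week 12 biopsy is done (Protocol 6.2, SAP 3.1).
5. Where does it appear? In the Group 2 column of the Week 12 treatment-related tables (SAP 3.5, 7.1).

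No provision in either document interrupts this chain.

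**Length of the undosed interval**

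Undosed full days = (study day of first dose) − 1. The nominal days for Visits 7 and 8 in Protocol Table 1 are 84 and 98.

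- First dose at Visit 7: 84 − 1 = 83 days per subject; 3 × 83 = 249 subject-days.
- First dose at Visit 8: 98 − 1 = 97 days per subject; 3 × 97 = 291 subject-days.

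This is about 12 to 14 weeks. Visit windows would move it by some days. Protocol 8.2 (Week 13) and footnote B (Visit 7, labelled Week 12, or Visit 8) do not describe the start identically. The trace does not depend on which is used.

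**Effect of one occurrence**

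Incidence = subjects with at least one treatment-related event ÷ subjects in the column. The assumptions are one affected subject, no other treatment-related event in Group 2, and the planned maximum of 9 and 3 subjects without replacements.

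- Group 2 column as written: 1/3 = 33.3%.
- Group 2 column with imputation tied to first dose: 0/3 = 0%.
- Group 1 minus Group 2 difference: lowered by 33.3 percentage points, whatever the Group 1 value.
- Overall column (SAP 7.1), if shown at Week 12: raised by 1/12 = 8.3 points.
- With only two or one controls enrolled, the Group 2 figure would be 1/2 = 50% or 1/1 = 100%.

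**Week 52 layout**

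SAP 3.5 lists five adverse event columns: Group 1 controlled, Group 1 noncontrolled, Group 2 noncontrolled, the two noncontrolled columns combined, and everything since pegcetacoplan began. None holds the Group 2 controlled portion.

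**The case against.** The strongest reply is that the situation should hardly arise. Protocol 11.2 requires a causality judgement for every event, Protocol 11.2.1 repeats that the investigator assesses each one, and Protocol 12.2.6 requires missing values to be reviewed and resolved before database lock. A blank field in one of at most three controls would have to survive all of these steps. The documents give no frequency of missing causality, so 33.3% is one hypothetical event over a denominator of three and not an expected error. The tables are descriptive, and a reader could compare them with the listing of all adverse events. All of this stands and limits the weight of the point. It does not make the rule correct: an imputation rule exists for the cases that survive review, and here it gives an answer that must be wrong.

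A second reply is that the missing listing sentence is only a drafting omission, since SAP 13.6.4 and 13.6.6 both put actual values in listings. That is the likely intention, but SAP 13.6.5 does not state it.

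A third reply concerns the remedy. Coding every Group 2 event before first dose as not related would overwrite causality that the investigator recorded. Partial dates also need care. SAP 13.6.3 sends incomplete start dates to rules built around Study Day 1 (SAP 13.6.2.1). An event known only to have started in the first-dose month, when that month is later than the month of Study Day 1, would be imputed to the first of the month. It could thus fall before dosing and lose a legitimate *Related*. Both objections are sound, and the fix is limited accordingly.

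**Conclusion.** The rule is wrong as written for undosed Group 2 subjects, and the point is minor. The error is confined to the descriptive Week 12 tables and possibly the treatment-related listing. The primary endpoint is untouched. The size shown assumes full 9:3 enrolment and a single affected subject.

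A reader might infer three stronger things that the documents do not support.

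- *That the Group 2 treatment-emergent window should start at first dose.* Starting at randomization is what makes the Week 12 comparison between groups possible, and Protocol 12.4 and SAP 7.1 agree on it. Protocol 11.2 calls pre-dose events pretreatment, but it does so in the section on recording and reporting and does not alter the tabulation definition.
- *That the Week 52 tables are contaminated as well.* They have no Group 2 controlled-portion column. SAP 3.5 builds the since-injection column from columns that include Group 2's noncontrolled one, which implies that the latter starts at first dose. The separate table shells hold the layout detail.
- *That a false treatment-related event is likely.* Nothing in the documents indicates how often causality will be missing.

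**What to change.** In SAP 13.6.5:

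1. Impute *Related* only when causality is missing and the event starts on or after the subject's first pegcetacoplan dose.
2. When causality is missing and a Group 2 event clearly starts before first dose, tabulate it as not related or not applicable.
3. Keep *Related* when an incomplete start date cannot place the event before first dose.
4. Leave any causality recorded by the investigator unchanged.
5. Add the counterpart of the SAP 13.6.4 sentence: imputed values in summaries, actual values in listings.

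Keep randomization as the start of the Group 2 treatment-emergent window.

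The cost is a few sentences in one SAP section, plus a programming condition on first-dose date with a check on whether the event start date is complete. It needs no new data and no protocol amendment, since the protocol's safety analysis section sets no causality imputation rule and leaves full analysis detail to the SAP.
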